Numerous studies exist speaking to the efficacy of automated reminder (i.e. notifying parents of needed immunizations) and recall (i.e. notifying parents of overdue immunizations) systems, including text messaging systems.^{1,2,3} Other studies show that the combination of texting and calls proves even more successful in reaching patients.³ These systems are more cost effective and efficient. Differences in the timing of reminders to schedule, as well as the message itself, has been shown to make a difference in the outcomes of reaching patients or scheduling appointments.⁴ However, there remains a need for research that identifies the degree to which combinations of patient reminder systems improve outcomes, especially the outcome of on-time immunization, and how these approaches differ by age of child.¹

Following the COVID-19 pandemic shut-down in which thousands of well child appointments were cancelled or delayed, the importance of a systematic outreach process became more critical. The traditional process is non-standardized and the efficacy of the work is both unknown and expensive. Our objective is to determine the effectiveness of varied outreach methods (e.g. automated reminder calls/text messages with or without personalized calls/texts, MyChart messaging) to children age 12-14 months, 4 years old, or 6-17 years old who are due for a WCC visit and don't have one scheduled in the next 45 days on the outcomes of appointment scheduling, appointment completion, and receipt of the MMR vaccination.

2. Design/Method

To achieve our objective, we will conduct a 2×2 factorial randomized controlled trial. Randomization is justified because 1) it is a rigorous approach to answer our question and 2) we do not have the resources or appointment availability to personally contact every patient who is eligible and have them schedule immediately.

Patient Population:

Patients are eligible for inclusion in this study if they are in one of four eligible groups:

12-14 months AND	4 years AND

• doesn't have a well visit scheduled in the next 45 days• have not yet received 12-month immunizations• have English and/or Spanish as preferred language	
• doesn't have a well visit scheduled in the next 45 days• has not had a well child visit in 365 days• have English and/or Spanish as preferred language

6-11 years AND	12-17 years AND

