PPC	Hi, this is [Staff First Name] from PPC. [Pt first name] is due for a check up. I'll call in a day or two to help schedule that appointment or you can walk in today to have your child seen! You can also call [contact], option 1 to schedule.	Hi, this is [First Name] from PPC. I noticed that [Child's First Name] is due for a check up. Can I schedule that for your right now? Alternate script for leaving a voice message: Hi, this is [First Name] from PPC. I noticed that [Child's First Name] is due for a check up. Sorry I missed you. Please call [contact], option 1 to schedule your appointment or walk in today to have your child seen.

*Scripts have been translated into Spanish versions by Interpreter Services

Response variables (outcomes):

- Appointment **was scheduled** within 2 weeks of intervention (Y/N) (date of actual appointment may be greater than 2 weeks from intervention)
- Appointment **was completed** within 8 weeks of intervention (Y/N). Appointment completed within 8 weeks of randomization will be used for group who does not receive any intervention.
- (Primary Outcome) Receipt of MMR by 15 months of age or receipt of 2nd MMR dose by 3 months after randomization (Y/N)
- Receipt of 1st COVID vaccination (ages 12-17 years) within 8 weeks of first intervention (Y/N)
- Family member receipt of COVID vaccination in our health system within 8 weeks of first intervention

Blocking: (controlling for factors that might influence the outcome)

- Age (12-14 months, 4 years)
- Clinic location (PPC, HPC, FPC)

Personal Contacts (12-14 months & 4-year-olds) Trial:

Randomization: Eligible patient will be identified by running a report in the electronic health record (EHR). We will run this report, stratified by clinic location, and randomly assign patients into one of the four groups created by our 2 X 2 design. Groups will receive their assigned intervention in one of four successive weeks with the sequence randomly assigned (see table below).

Replication: We will conduct a total of 3 trials, repeating the randomization procedure every 4 weeks to identify children who become eligible: Weeks 1-4 = trial #1, weeks 5-8 = trial #2, weeks 9-12 = trial #3.

Outreach Methods Study Protocol & SAP

Version 1.1, 1/14/22

	1 automated message sent	2 automated messages sent
0 personal contact attempt	Message sent on Thu (weeks 3, 5, 10)	Message sent on Thu & Fri (weeks 4, 6, 12)

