1 personal contact attempt	Above plus attempt Mon – Fri of following week (weeks 2, 7, 11)	Above plus attempt Mon – Fri of following week (weeks 1, 8, 9)

MyChart and Televox Trials (6-17 years old):

Randomization: Eligible patients will be identified by running a report in the electronic health record (EHR). We will run this report, stratified by clinic location, and randomly assign patients into one of the study groups as described above. Groups will receive their assigned intervention in one of four successive weeks with the sequence randomly assigned (see table below).

We will randomize children who are eligible and implement interventions for each trial : Weeks 1-3 = Televox Trial 12-17yo, Weeks 4-7 = Televox Trial 6-11yo, Weeks 8-10 = MyChart Trial.

MyChart Trial:

	no message	1 MyChart message sent	2 MyChart messages (e.g. Mon and Thurs)
Standard Message	No intervention	Week A	Week B
Tailored Message		Week A	Week B

Televox (6-11yo) Trial:

no message	Low Tailored Message 2 automated standard messages sent (e.g. Thu, Fri) (weeks C, C)	High Tailored Message 2 automated tailored messages sent (e.g. Thu, Fri) (weeks D, D)
-------------------	--	---

Televox (12-17yo) Trial:

no message	Low Tailored Message 2 automated tailored messages sent (e.g. Thu, Fri) (week A)	COVID Tailored Message 2 automated messages sent (e.g. Thu, Fri) (week B)
-------------------	--	---

Of note, automated messages and/or personal contact attempts will not be completed if the parent schedules an appointment after being randomized but before receiving the intervention.

Covariates for logistic regression: (factors that might influence the outcome if not balanced across groups)

1. Child age at the time of randomization (rationale: visits are less frequent for children age 4 years)
2. Parent preference for call vs. text mode of contact (rationale: calls may be more likely to get blocked than texts)
3. Parent with activated MyChart account (Y/N) (rationale: not dependent on calling scheduling center to make appointment)

4. Access to appointment: Number of days to 3rd next available appointment at patient's clinic at time their first automated message is sent
5. Patient receipt of any past immunizations (Y/N) (rationale: vaccine refusing parents will be unlikely to change even if they return for well child check)
6. School-age vs. adolescent patient age (rationale: adolescents less likely to get yearly check-ups)
7. Historical no-show rate

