For the Personal Contact (12-14 mo & 4 years old) trials, we will conduct intent-to-treat analyses using logistic regression models (without adjusting for covariates) for each of our three binary outcomes: completed appointment within 2 weeks, completed appointment within 8 weeks, receipt of MMR by 15 months of age or receipt of 2nd MMR by 3 months after randomization. We will do pair-wise comparison among the 4 groups and adjust p value of each comparison for multiplicity. If participants in the 4 groups differ on potential covariates, we will conduct additional analyses adjusted for these variables.

For the MyChart and Televox Trials (6-17 years old), we will conduct intent-to-treat analyses using logistic regression models (without adjusting for covariates) for each of the binary outcomes: scheduled appointment within 2 weeks, completed appointment within 8 weeks, receipt of 1st dose of COVID vaccination (age 12-17 years) within 8 weeks, family member receipt of COVID vaccination within 8 weeks. We will do pair-wise comparison among the treatment groups and adjust p value of each comparison for multiplicity. If participants differ in potential covariates across treatment groups, we will conduct additional analyses adjusted for these variables. We will explore non-inferiority analysis for comparison the two groups that are expected to have similar appointment scheduled and completion rate in the MyChart trial.

We will also conduct per-protocol analyses according to the interventions actually received by the participants, recognizing that actual intervention received could be different from initial randomized intervention. For example, a parent allocated to group A might schedule an appointment after receiving the automated message and therefore would not receive a personalized contact attempt. In addition, we may explore potential interaction between the two interventions as a secondary analysis. All analysis will be conducted using SAS version 9.4.

Duration

The study will begin upon IRB approval and continue through December 31, 2022. During this time, we will discuss the significance of data, potential future projects and dissemination of results.

Process of Obtaining Consent

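### Personal Contacts trial: age group is listed as a blocking factor, but allocation is stratified by clinic only and the main model adjusts for neither, so some precision is given up

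*Combined protocol and SAP*

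**What the plan says.** All of this is in the protocol, section 2 (Design/Method), and concerns the Personal Contacts trial unless noted.

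- **Blocking.** The list is headed "Blocking: (controlling for factors that might influence the outcome" and has two entries: "Age (12-14 months, 4 years" and "Clinic location (PPC, HPC, FPC". Those age levels are the ones used in the Personal Contacts trial.
- **Randomization**, immediately below: "We will run this report, stratified by clinic location, and randomly assign patients into one of the four groups". Age is not named here or in any other allocation statement. The procedure is repeated every four weeks, for three replications. No block size is given for this trial.
- **Primary outcome**, under Response variables: "Receipt of MMR by 15 months of age or receipt of 2nd MMR dose by 3 months after randomization (Y/N".
- **Eligibility** for the 12-14 month group includes "have not yet received 12-month immunizations".
- **Covariates for logistic regression.** The first entry is "Child age at the time of randomization (rationale: visits are less frequent for children age 4 years".
- **Analysis.** The main intent-to-treat analysis is described as "using logistic regression models (without adjusting for covariates) for each of our three binary outcomes". Child age group is among the characteristics compared across the four groups by chi-square test. Adjusted models are additional and run only if the groups differ.

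The separate SAP gives clinic stratification with a block size of 3, but only for the trial in 12-17 year olds, so it does not settle the matter.

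**The concern.** The Blocking list and the randomization paragraph do not agree. Someone building the allocation list from the randomization paragraph alone would leave out a factor that the protocol says it controls.

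Age group is a natural factor to control here. A child of 12-14 months without the 12-month immunizations is judged on MMR by 15 months of age. The second-dose criterion, with its three-month window, fits the 4-year-olds. The protocol does not spell out this mapping, but it follows clearly from eligibility. The two groups are therefore scored on different doses over different windows, and the protocol's own covariate rationale expects visit behaviour to differ by age.

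What is at stake is precision. If MMR rates differ by age, variation between age groups stays in the error of the unadjusted comparison, and it appears in any one randomization as a chance difference in age mix between arms. Clinic has a related gap: it is used in allocation but left out of the main model, so the reported standard errors would not reflect whatever that stratification gains.

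**Working it through.** **Inputs from the protocol (Power/Sample Size).** Expected MMR rates are C 20%, B 35%, A 50% and AB 65%; alpha 0.05, power 80%; 167 per group, 4 x 167 = 668. I take alpha as two-sided, which reproduces the figures.

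**Assumptions, not in the documents.** Age split 50:50 (30-70% where stated). Age-specific MMR rates 15 to 30 points apart. A 5% threshold for the chi-square balance check.

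**1. The plan's own figure.** n = [p1(1-p1) + p2(1-p2)] x (1.960 + 0.842)^2 / d^2. For A vs B: (0.25 + 0.2275) x 7.849 / 0.0225 = 166.6, so 167. The same formula returns all six tabulated sizes (36, 136, 167, 167, 40, 16). They are built on marginal rates, so between-age variation is already inside them.

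**2. Share of outcome variance between age groups.** One minus the mean within-age p(1-p) over the marginal p(1-p).
- 20% vs 35%: 1 - 0.19375/0.199375 = 2.8%.
- 20% vs 50%: 1 - 0.205/0.2275 = 9.9%.

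**3. The same quantity seen as chance imbalance.** The SD of the difference in age mix between two arms is sqrt(2 x 0.25/167) = 0.0547. Multiplied by a rate gap of 15 or 30 points, this is 0.82 or 1.64 points on the contrast. The unadjusted standard error for A vs B is sqrt(0.4775/167) = 5.35 points. The ratios of variances are (0.82/5.35)^2 = 2.4% and (1.64/5.35)^2 = 9.4%. Steps 2 and 3 describe one loss in two ways and must not be added.

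**4. Power for A vs B.** The unadjusted test has 0.15/0.0535 = 2.805, and 2.805 - 1.960 = 0.845, giving 80%. With the between-age variance removed:
- 15-point gap: 2.805/sqrt(1 - 0.024) = 2.84, power about 81%.
- 30-point gap: 2.805/sqrt(1 - 0.094) = 2.95, power about 84%.

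**5. Would the planned balance check catch an imbalance?** With a largest gap of 10 points between arms, chi-square is greatest when two arms sit 5 points above the mean and two sit 5 points below: 4 x 167 x 0.05^2 / 0.25 = 6.7. The 5% critical value on 3 df is 7.81, so such a gap does not trigger adjustment. In 200,000 simulated randomizations of four arms of 167, a largest gap of 10 points or more occurred in about 20-27%, for 30-70% of children aged 12-14 months.

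**The case against.** **The randomization sentence may simply be incomplete.** The Blocking list does include age, and the sentence is almost the same as the one for the MyChart and Televox trials. A reader might infer that the arms are definitely not blocked on age. The documents do not support that. They establish only that the passages disagree and that the procedure as written omits age.

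**The plan does not ignore age.** It is the first listed covariate, it is checked across the four groups, and it is adjusted for if they differ. This stands, but it is a secondary analysis that depends on a check which step 5 shows can miss a 10-point gap.

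**A reader might infer that the result would be biased or the trial underpowered.** Neither follows. Randomization balances age in expectation, ordinary standard errors already contain the chance imbalance, and 167 per group was computed from marginal rates. Type I error and planned power are intact, and the protocol expects to exceed 668.

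**A reader might infer that age is the strongest stratifier available.** The documents give no age-specific MMR rates, so it cannot be ranked. Past immunization receipt, also on the covariate list, is a plausible rival.

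**The logistic model does not deliver the gain as a smaller standard error.** Adding age changes the odds ratio from marginal to conditional. In simulations of A vs B with a 50:50 age split, the mean standard error of the log odds ratio rose from 0.225 to about 0.229 (15-point gap) or 0.239 (30-point gap), while power gained between nothing and about 3 points. This stands. It is why the gain is stated as an upper limit and why the estimand needs a name.

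**Conclusion.** The point holds as a minor one. The protocol names age group and clinic as factors to be controlled, stratifies allocation by clinic only as written, and uses neither in the main model. The conditional adjustment softens this but does not remove it.

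The loss is one of precision: about 3-10% of outcome variance, worth at most 1 to 4 points of power on the A vs B and A vs AB contrasts that set the sample size. These figures rest on the assumed 50:50 age split and 15 to 30 point difference in MMR rates. With a smaller difference the gain is negligible. What makes the change worthwhile is that both factors are already to hand and the text has to be reconciled anyway.

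**What to change.** 1. **Reconcile the Blocking list and the randomization paragraph.** State that allocation in each replication is stratified by clinic and age group, and give the block size. The documents do not say whether this trial has already been randomized. If it has, report what was actually done.
2. **Prespecify age group and clinic as terms in the primary model**, in place of adjustment triggered by the chi-square check. This remains possible after allocation if outcomes have not been analysed. It also matters if age is stratified, because otherwise the gain does not appear in the reported standard errors.
3. **Name the estimand.** Either state that the adjusted odds ratio is conditional on age group and clinic, or report a standardized risk difference from the same model.

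**Cost.** Small but not nil. No new data are needed, since age and clinic are required to identify eligible children. Allocation would use 3 x 2 = 6 strata per replication, or 18 cells over three replications. At 668 children that averages 668/18, about 37 per cell, though later replications take only newly eligible children and some cells may be small. The sample size does not change.

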8. Community rates of COVID based on 7 day moving average.

Power/Sample Size

Personal Contacts (12-14 month & 4-year-olds) Trial:

We based our hypotheses (see table, below) on a systematic review's pooled estimates of effect size for automated messages and personalized calls finding 37% and 40% of children, respectively, completed immunizations.¹ Because of the significant cost involved in making personal contacts, the minimal difference in outcome that would make it worth the effort is high.

Hypotheses	% of children who receive MMR by 15 months of age	
	1 automated message sent	2 automated messages sent
0 personal attempts	20% ^C	35% ^B
1 personal attempt	50% ^A	65% ^{AB}

We calculated sample size needed per group to detect a difference for each of the contrasts below with alpha of 0.05 and power of 80%.

Contrast	Sample Size per Group
A vs C	36
B vs C	136
A vs. B	167
A vs. AB	167
B vs. AB	40
C vs. AB	16

To fully power the 2 X 2 factorial trial, we estimate needing 167 per group X 4 groups = 668 total subjects. There are currently 712 children eligible for the study. More will become eligible every month so we expect to far exceed the required sample size after 3 replications. If needed, we could increase the number of replications of the trial to reach the targeted sample size. We acknowledge that we are not powered to precisely estimate any interactions between interventions.

MyChart Trial:

In hypothesis testing for 0 message vs. 1 message vs. 2 messages, we will do the testing in a fixed sequence - test 2 messages vs. 0 message first, only if it is significant then test 2 messages vs. 1 message, thus the type I error rate of 0.05 is retained. Since the hypothesis testing of 2 messages vs. 0 message would be considered easier to achieve than the hypothesis testing of 2 messages vs. 1 message, the power analysis for this trial should be based on the design of (standard message vs. tailored message) by (1 message vs. 2 messages). We based our hypotheses (see table, below) on previous work indicating approximately 20% WCC appointment completion on automated text reminders. We anticipate that a tailored message increases the WCC appointment completion rate by another 10%.

Hypotheses		% of children complete WCC within 8 weeks

	No message	1 automated message sent	2 automated messages sent
Standard Message	2%	10% ^C	20% ^B
Tailored Message		20% ^A	30% ^{AB}

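### The Personal Contacts models omit randomization cycle, a factor the trial randomizes within; adding it improves efficiency modestly and does not correct a bias

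*Combined protocol and SAP*

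**What the plan says.** **Randomization.** In the protocol's Design/Method section, the Replication paragraph for the Personal Contacts trial reads: "We will conduct a total of 3 trials, repeating the randomization procedure every 4 weeks to identify children who become eligible". Weeks 1-4, 5-8 and 9-12 are labelled trials 1, 2 and 3. The Randomization paragraph says of the eligibility report "We will run this report, stratified by clinic location", and that the team will "randomly assign patients into one of the four groups created by our 2 X 2 design". All four arms are therefore allocated in every cycle. Age is also listed under Blocking. No allocation ratio or block size is stated for this trial.

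**Sample size.** Under Power/Sample Size: "we estimate needing 167 per group X 4 groups = 668 total subjects". Then: "There are currently 712 children eligible for the study". And: "More will become eligible every month so we expect to far exceed the required sample size after 3 replications". The cycles accrue to one total, and further replications are allowed if needed. That the cycles will be pooled is an inference from this; the Analysis section does not say so.

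**Analysis.** For this trial "we will conduct intent-to-treat analyses using logistic regression models (without adjusting for covariates) for each of our three binary outcomes", followed by pairwise comparisons with multiplicity-adjusted p-values. Adjusted models are additional and are fitted only if the arms differ on the potential covariates. Cycle is not among the eight items under Covariates for logistic regression. The separate SAP covers only the 12-17-year trial and adds nothing on this point.

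**The concern.** Each child is allocated within one 4-week cycle, so cycle is in effect a randomization stratum. The usual practice is to carry such a factor into the model; here neither the primary models nor the conditional adjusted ones include it.

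The documents suggest why outcome rates could differ by cycle. Cycle 1 draws on the existing eligible pool, and later cycles add children as they become eligible. Infants enter at 12-14 months, and their primary outcome is MMR by a fixed age of 15 months. A standing pool can span that whole age window, whereas newly eligible infants may more often have just turned 12 months and so have longer to reach the deadline. This is plausible but not documented.

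If rates do differ, an unadjusted comparison gives up some power. When the arms are balanced within cycles, its standard error is also larger than the design warrants, so the test rejects less often than 5% under the null.

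**Working it through.** **1. The plan's own figure.** Inputs from Power/Sample Size: rates C 20%, B 35%, A 50%, AB 65%; alpha 0.05 (taken as two-sided; the text does not say) and 80% power. With

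n = (1.960 + 0.842)² × [p1(1−p1) + p2(1−p2)] / (p1−p2)²,

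A vs AB gives 7.849 × (0.2500 + 0.2275) / 0.0225 = 166.6, so 167. The same formula returns the plan's 36, 136, 167, 40 and 16 for the other contrasts, and 4 × 167 = 668. A cycle term does not alter these figures.

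**2. Assumptions.** The documents give neither cycle sizes nor cycle-specific rates. I took 167 per arm, split 56/56/55 over three cycles, with control rates of 35% throughout, 25/35/45%, or 15/35/55%. Each averages about 35%. The alternative is a common odds ratio that raises the overall rate by 15 points.

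**3. Type I error in closed form, arms balanced within cycles.** The unadjusted test uses the variance p̄(1−p̄) = 0.35 × 0.65 = 0.2275. The true variance of the difference depends on the average of p(1−p) over cycles.

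- 25/35/45%: (0.1875 + 0.2275 + 0.2475)/3 = 0.2208. The effective critical value is 1.96 × √(0.2275/0.2208) = 1.99, a type I error of about 0.047.
- 15/35/55%: (0.1275 + 0.2275 + 0.2475)/3 = 0.2008. The critical value is 1.96 × √(0.2275/0.2008) = 2.09, a type I error of about 0.037.

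**4. Simulation.** One pairwise contrast, 200,000 runs per scenario. The pooled unadjusted test is compared with a cycle-stratified Cochran-Mantel-Haenszel test, which stands in for a logistic model with a cycle factor.

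| Control rates by cycle | Allocation within cycle | Type I, unadjusted | Type I, stratified | Power, unadjusted | Power, stratified |
|---|---|---|---|---|---|
| 35/35/35% | equal | 0.0496 | 0.0495 | 0.8022 | 0.8023 |
| 35/35/35% | simple, unblocked | 0.0494 | 0.0493 | 0.7947 | 0.7913 |
| 25/35/45% | equal | 0.0458 | 0.0499 | 0.8040 | 0.8055 |
| 25/35/45% | simple, unblocked | 0.0504 | 0.0495 | 0.7954 | 0.8038 |
| 15/35/55% | equal | 0.0365 | 0.0500 | 0.8178 | 0.8470 |
| 15/35/55% | simple, unblocked | 0.0505 | 0.0493 | 0.7960 | 0.8435 |

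The power gain is 0.15 to 0.84 points under 25/35/45% and 2.9 to 4.8 points under 15/35/55%. If rates do not differ and allocation is unblocked, stratifying loses 0.3 points. Under the null the mean difference between arms was within 0.0003 of zero in every row.

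**5. A front-loaded first cycle.** If all 712 entered cycle 1 (712/4 = 178 per arm) and, by assumption, 100 more children entered each later cycle (25 per arm), with control rates of 30/50/50%, power goes from 0.9093 to 0.9107 (equal allocation) or from 0.9036 to 0.9110 (unblocked). Both gains are under 1 point.

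**6. When bias would arise.** Only if allocation shares changed between cycles. Suppose one arm had 62/56/49 children by cycle and the other 49/56/62, with no treatment effect. At 25/35/45% the difference is 13 × (0.25 − 0.45)/167 = −1.6 points, with simulated unadjusted type I error 0.057. At 15/35/55% it is 13 × (0.15 − 0.55)/167 = −3.1 points, with 0.075. The stratified test stays at 0.050. No passage plans such a change.

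**7. Effect on the estimand.** In the equal-allocation alternatives the marginal odds ratio is 1.86. The within-cycle odds ratio is 1.90 (25/35/45%) or 2.03 (15/35/55%).

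**8. What a cycle term leaves untouched.** The timetable puts C in weeks 3, 5, 10; B in 4, 6, 12; A in 2, 7, 11; AB in 1, 8, 9. Subtracting 0, 4 and 8 gives positions within the cycle: C 3, 1, 2; B 4, 2, 4; A 2, 3, 3; AB 1, 4, 1. In each cycle every week belongs to a single arm, so arm and delivery week are confounded inside the cycle whether or not cycle is in the model.

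**The case against.** The strongest reply is that an unadjusted primary model is a valid prespecified choice. All four arms are randomized in every cycle, and the 167 × 4 calculation implies equal allocation. Differences between cycles therefore cannot bias the contrasts, and chance imbalance is already covered by the test: unadjusted type I error is 0.050 under simple randomization. This stands. A reader might infer from the unstated block size that cycle differences leak into the arm effects. The documents do not support that, because leakage needs a ratio that varies by cycle.

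Three other strong readings also fail. The cycles are not different populations, since the eligibility criteria are the same throughout and only the case mix may shift. The 712 are described as eligible, not as a long-overdue backlog. And cycle variation does not remain in an error term, because logistic regression has no residual variance to inflate; the omission shows up as a marginal odds ratio nearer 1 and some lost power.

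The reply also notes that appointment access and the community COVID rate vary with calendar time, and that child age is a listed covariate. They are at best partial proxies for cycle and enter only if the arms happen to differ. If recruitment does far exceed 668, there is also less power left to gain, as step 5 of the working shows. Finally, a cycle term changes the odds ratio from marginal to conditional. That is a real but small cost, met by reporting both.

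**Conclusion.** The point holds as a minor specification and efficiency gap. The plan randomizes within three cycles, counts them toward one total, and analyses them without cycle. The benefit of adding it is under 1 point of power if control rates rise moderately over the cycles (25/35/45%) and about 3 to 5 points if they rise steeply (15/35/55%). It also removes a mild conservatism when arms are balanced within cycles (type I error 0.046 and 0.037 respectively).

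These sizes rest on assumed cycle rates and cycle sizes, on pooling that is inferred, and on a single contrast tested at 0.05. The planned multiplicity adjustment would lower the absolute power figures. If rates do not differ by cycle, there is nothing to gain. The validity of the planned contrasts is not in question on this ground, provided the allocation ratio stays constant.

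**What to change.** In the protocol's Analysis section, prespecify randomization cycle as a fixed factor in every Personal Contacts logistic model, with one level per replication actually run, together with the clinic stratum. Enter them as main effects, as CLASS variables in SAS. If age was also used to block the allocation, treat it the same way. State the allocation ratio and that it is constant across cycles, since the absence of bias depends on it.

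The cost is a sentence or two and 2 degrees of freedom for cycle with three cycles. No new data are needed, because cycle is fixed at randomization. The odds ratio becomes conditional on cycle, so report the unadjusted result beside it, and show arm results by cycle descriptively. The confounding of arm with delivery week inside each cycle is a separate matter that this change does not address.
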